4.14.3.7.1 Inter-reader agreement analysis

The Cohen's kappa statistic will be used to assess pairwise agreement between 2 readers including 95% exact CIs giving three kappa statistics (SAS® nomenclature: simple kappa). In addition, the Fleiss' kappa across the 3 readers including 95% (approximate) CIs will be shown (SAS® nomenclature: overall kappa Coefficient).

This same calculation will be repeated for the regions:

- Prostate/Prostate Bed
- Pelvic Lymph Nodes
- Other
 - Other: Lymph nodes outside pelvis
 - Other: Soft Tissue/parenchyma
 - Other: Bones.

4.14.3.7.2 Intra-reader agreement analysis

Cohen's Kappa will be used to assess intra-reader agreements in the first read and the repeat read of 10% of the randomly selected images for each of the three readers.

This same calculation will be repeated for the regions:

- Prostate/Prostate Bed
- Pelvic Lymph Nodes
- Other
 - Other: Lymph nodes outside pelvis
 - Other: Soft Tissue/parenchyma
 - Other: Bones.

4.14.4 Exploratory Efficacy Variables

4.14.4.1 Diagnostic performance (sensitivity and specificity) of rhPSMA-7.3 (¹⁸F) PET for detecting pelvic LN metastases compared to surgical pathology on a regional level.

This analysis will be performed using the EAP on all patients who were not diagnosed as M1 in the rhPSMA-7.3 (¹⁸F) PET imaging and for all sides where surgical pathology was performed.

PAREXEL International

Blue Earth Diagnostics
BED-PSMA-301

Statistical Analysis Plan

In this analysis, each patient will be considered as a cluster, with left hemi-pelvis and right hemi-pelvis considered as two observations within each cluster. Regions will be classified according to Table 3.

The descriptive parts of the primary analysis; cross table, sensitivity and specificity, will be repeated using region level analysis.

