5.3 Exploratory Efficacy Endpoints

1. Diagnostic performance (sensitivity and specificity) of rhPSMA-7.3 (¹⁸F) PET for detecting pelvic LN metastases compared to surgical pathology on a regional level.
2. Diagnostic performance of rhPSMA-7.3 (¹⁸F) PET in patients with a) pelvic LN metastatic deposits <5 mm (short axis) and LN metastatic deposits \geq 5 mm (short axis) and b) pelvic LN metastatic deposits <10 mm (short axis) and LN metastatic deposits \geq 10 mm (short axis).

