16.1 Data Sets Analyzed

All enrolled patients: all patients who signed the informed consent form.

Full Analysis Set (FAS): all patients who were scheduled to receive the rhPSMA-7.3 (¹⁸F) injection by meeting the inclusion/exclusion criteria.

Full Safety Population (FSP): all patients who received the rhPSMA-7.3 (¹⁸F) injection.

Efficacy Analysis Population (EAP): all patients who received rhPSMA-7.3 (¹⁸F) injection with a PET scan and who got through RP and PLND.

Per Protocol Population (PP): All evaluable patients in the EAP population.

The primary analysis will be based on the EAP. The FSP will be used for all safety summaries.

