4.5 Analysis Sets

All enrolled patients: all patients who signed the informed consent form.

Full Analysis Set (FAS): all patients who were scheduled to receive the rhPSMA-7.3 (¹⁸F) injection having met the inclusion/exclusion criteria.

Full Safety Population (FSP): all patients who received the rhPSMA-7.3 (¹⁸F) injection.

Efficacy Analysis Population (EAP): all patients who received rhPSMA-7.3 (¹⁸F) injection followed by a PET/CT scan and who underwent RP and PLND.

Extended Efficacy Population (EEP): all patients who received rhPSMA-7.3 (¹⁸F) injection followed by a PET/CT scan. This population includes M0 and M1 patients independent of performance of RP and PLND and will be used for M1 related efficacy and Kappa statistics.

Per Protocol Population (PP): All patients in the EAP population who have histology available from surgery that allows SoT determination, and without any major protocol deviations that will affect the evaluations of the PET scan or histology.

The primary analysis will be based on the EAP. The FSP will be used for all safety summaries.

Upon database release, protocol deviation and analysis set outputs will be produced and will be to BED for review. An analysis set classification meeting will be arranged to discuss the outputs and to decide which patients and/or patient data will be excluded from certain analyses. Decisions made regarding the exclusion of patients and/or patient data from the analyses, and the agreement of population inclusion for each patient, will be made prior to database lock and will be documented and approved by the Sponsor.

A by-patient listing of analysis set details will be provided. This listing will include: center, country, patient identifier, and inclusion/exclusion flag for each set and reason for exclusion from

PAREXEL International

Blue Earth Diagnostics
BED-PSMA-301

Statistical Analysis Plan

each set. All enrolled patients will appear on this listing. If patient data have been partially excluded, visit will also appear on this listing.

The number and percentage of patients in each population will be provided using all enrolled patients.

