4.10 Biopsy/Surgery

If the rhPSMA-7.3 (¹⁸F) PET shows M1 metastatic disease, the patient will be asked to undergo a biopsy or confirmatory imaging of the PET-positive lesion(s) to confirm the presence of a metastasis. If a surgical intervention of this lesion is carried out as part of the treatment, this may substitute for a biopsy. If the patient has proven M1 metastatic disease, the disease management may be altered, based on the responsible physician's clinical judgement. This change in disease management will be documented on the eCRF.

If rhPSMA-7.3 (¹⁸F) PET does not detect M1 disease, the patient will undergo the scheduled RP and PLND. In patients without M1 lesions identified and in whom the patient and physician believe, after obtaining the results of the rhPSMA-7.3 (¹⁸F) PET, that EBRT would be a better therapeutic option than surgery, the patient may proceed to EBRT and the rationale for this change of disease management will be documented on the eCRF.

PAREXEL International

Blue Earth Diagnostics
BED-PSMA-301

Statistical Analysis Plan

The regional PLND must be performed by a suitably qualified surgeon and should include, at minimum, resection of lymphatic tissue for histological analysis from the following nodal groups: 1) hypogastric (internal iliac), 2) external iliac, and 3) obturator LNs. Extended LN dissection may be performed if clinically appropriate and the anatomical regions (e.g. presacral, common iliac, peri-rectal) with left/right designations, should be recorded on the eCRF. The location of the dissected material shall be marked in order to allow matching with their anatomical origin (left and right pelvis); the left and the right side of the specimen shall be clearly marked. The dissected LNs will be sectioned and analyzed by a pathologist for the presence or absence of PCa according to standard of care at the clinical site. The number of lymph nodes sampled and found positive for PCa will be registered and summarized.

Patients with PET M1 will be summarized using the EEP by confirmatory method(s), result of confirmation, change in disease management, surgery (radical prostatectomy and pelvic lymph node dissection) performed, Lymph node dissection and (additional) treatment received. All counts will be presented including percentage of patients categorized as PET M1.

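### The exploratory regional analysis excludes operated patients called M1 on the study PET, without a stated reason and without saying whose M1 call applies

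*SAP*

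**What the plan says.** The protocol (5.3) defines the first exploratory endpoint as sensitivity and specificity "for detecting pelvic LN metastases compared to surgical pathology on a regional level". It sets no condition on M status.

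SAP 4.14.4.1 adds two conditions. The first concerns patients: the analysis is run in the EAP "on all patients who were not diagnosed as M1 in the" study PET. The second concerns sides: "and for all sides where surgical pathology was performed". The same section then says that the descriptive parts of the primary analysis are to be repeated at region level.

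The EAP is defined in SAP 4.5 by injection "followed by a PET/CT scan and who underwent RP and PLND", and in Protocol 16.1 as "all patients who received rhPSMA-7.3 (¹⁸F) injection with a PET scan and who got through RP and PLND". Neither definition mentions M status. SAP 4.5 also states: "The primary analysis will be based on the EAP".

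**The concern.** Sensitivity and specificity should be estimated in patients chosen without regard to the result of the test under study, as far as the design allows. Here an operated patient who has nodal pathology, and who counts in the primary analysis, is removed from the regional analysis because the same PET scan was read as M1.

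Three things are at stake:

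- Evaluable regions with a reference standard are discarded.
- The regional result describes a different group of patients from the patient-level result that it is meant to repeat.
- A programmer must decide whose M1 call to use. If it is each blinded reader's own call, the three readers are assessed on different sets of regions, and differences between readers mix reading performance with case mix.

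**Working it through.** **The plan's own figures (context only).** The documents give no figure for the regional analysis. The stated 90% power of the two primary tests (SAP 4.16) is reproduced with exact one-sided binomial tests at 0.025:

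- Sensitivity: n = 75, goal 22.5%, assumed 40%. Reject at 25 or more; attained level 0.0207; power 90.4%.
- Specificity: n = 225, goal 82.5%, assumed 90%. Reject at 197 or more; attained level 0.0246; power 90.6%.

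**Can an operated patient carry a PET-M1 call?** Yes, by three routes:

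1. SAP 4.10 plans a summary of PET-M1 patients that includes "surgery (radical prostatectomy and pelvic lymph node dissection) performed".
2. Under Protocol 9.1.7 and SAP 4.10, even proven M1 disease leads only to a possible change of management.
3. The local read guides patient management (Protocol 9.1.6), while efficacy uses three central readers. SAP 4.12 (item 3) and SAP 4.14.3.1 both provide for a blinded reader calling M1 where the site did not. Such a patient, M0 on the local read, goes on to the scheduled surgery unless EBRT is chosen, and so can enter the EAP.

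**Is the restriction declared?** SAP 4.17 records the added Extended Efficacy Population, the removal of the second exploratory endpoint and two wording changes. It does not record an M1 restriction on the first exploratory endpoint.

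**Illustrative size.** The number of operated PET-M1 patients is not given, so it is assumed. Patient-level counts stand in for regions. From SAP 4.16, the full EAP has 75 pN1 patients with sensitivity 40% (30 TP) and 225 pN0 patients with specificity 90% (202.5 expected TN). Remove m patients, half of them pN1, with nodal sensitivity s and specificity c among those removed:

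- Restricted sensitivity = (30 - s × m/2) / (75 - m/2)
- Restricted specificity = (202.5 - c × m/2) / (225 - m/2)

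| m | s = 70% | s = 90% | Shift from 40% (points) |
|---|---|---|---|
| 3 | 28.95/73.5 = 39.4% | 28.65/73.5 = 39.0% | -0.6 to -1.0 |
| 8 | 27.2/71 = 38.3% | 26.4/71 = 37.2% | -1.7 to -2.8 |
| 15 | 24.75/67.5 = 36.7% | 23.25/67.5 = 34.4% | -3.3 to -5.6 |

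For specificity, c = 90% gives no change. With c = 70% and m = 15, 197.25/217.5 = 90.7%, a rise of 0.7 points.

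The direction depends on s. With s = 40% there is no shift. With s = 20% and m = 8, (30 - 0.8)/71 = 41.1%, a rise of 1.1 points. The pN1 share matters too: at m = 15 and s = 70% to 90%, a share of one quarter gives -1.6 to -2.6 points and a share of three quarters gives -5.3 to -8.8.

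**The case against.** The best defence has four parts.

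- **Weight.** The endpoint is exploratory and descriptive, with no test or performance goal. This stands, and it limits the point to a minor one.
- **Authority.** Protocol 16 and 16.5 leave modifications and detail to the SAP, and SAP 1 says that the SAP prevails where the two differ. So the mismatch with the protocol is not in itself an error. The missing rationale and the missing entry in SAP 4.17 remain.
- **Few patients.** SAP 4.17 gives patients with M1 lesions as an example of those without surgery, and SAP 4.16 counts M1 disease among the reasons for losing surgical patients. The number may well be small. But if it is zero the clause does nothing, and if it is not zero the clause drops usable data.
- **The M1 read can be inferred.** SAP 2.3 ties the objective to the central read, SAP 4.14.1 runs analyses per reader and for the majority, and SAP 4.14.3.1 defines M1 per reader. A per-reader reading is therefore the natural one, but SAP 4.14.4.1 does not say so, and that reading is the one that makes the population vary by reader. Reader-specific denominators are not a fault in themselves; PPV and NPV have them by definition.

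A reader might also infer that the restriction biases regional sensitivity downward by a material amount, on the ground that PET-M1 patients tend to have visible positive nodes. The documents do not show this for those who are operated. M1 confirmation is required before treatment and proven M1 may divert the patient, so the operated group may be enriched for M1 calls that were refuted or were made only centrally. Its nodal profile is unknown.

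**Conclusion.** The point holds as a minor one. SAP 4.14.4.1 excludes operated patients from an accuracy analysis because of an index-test result. The exclusion is absent from the EAP, the primary analysis and the protocol endpoint; it is unexplained and unlisted, and the M1 read is unnamed.

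The shift of -0.6 to -5.6 points rests on assumed values: 3 to 15 such patients, half pN1, nodal sensitivity of 70% to 90% among them, and patient-level counts in place of regions. It shows scale only. Neither size nor direction follows from the documents.

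Two further inferences should be resisted:

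- Not every operated PET-M1 patient need have pathology on both sides. SAP 4.13 has a category for a missing hemipelvis, and SAP 4.14.1.2 has a rule for missing results.
- Removing the clause does not make the regional and primary results fully comparable, nor does it free the analysis of all PET-driven selection. Sides without pathology are omitted here, whereas SAP 4.14.1.2 assigns them the worst value. The EAP is itself shaped by the local PET read, which can steer patients away from surgery.

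**What to change.** In SAP 4.14.4.1, delete the M1 condition, so that the main regional analysis uses all EAP patients and all sides with surgical pathology for every reader. If a PET-M0 result is wanted, add it as a supplementary row and state which M1 read defines it (site, each blinded reader, or majority). If any restriction is kept, give the reason and list it in SAP 4.17. In the table footnote, state the remaining difference in how sides without pathology are handled.

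The cost is one phrase, one footnote and one optional table row. No new data are needed.

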4.15 Safety Evaluation

All safety summaries and analyses will be based upon the FSP as defined in Section 4.5.

4.15.1 Adverse Events

For AEs and Serious AEs (SAEs), the MedDRA Version 22.1 or later will be used to code the reported events.

Treatment-emergent adverse events (TEAEs) will be tabulated and are defined as those AEs that either start or worsen in severity on or after the date/time of IP administration and on or before Day 4.

Where dates are missing or partially missing, AEs will be assumed to be treatment-emergent, unless there is clear evidence (through comparison of partial dates) to suggest that the AE started prior to IP administration or more than 4 days after IP administration.

In particular this means the following rules will be applied until a classification is given:

1. An AE with a missing start date and missing end date will be a TEAE
2. An AE with a missing start date and end date after IP administration will be TEAE
3. A start date with a missing year but month present will be assumed to have a year such that the start date is after informed consent and before Day 90. If these rules conflict then the rule 'after informed consent' prevails.
4. An AE will not be a TEAE if the start date is incomplete and
 - a. The end date of the AE is before the dosing date
 - b. The end date/time of an AE is before the dosing date/time
 - c. The day of the AE end date is missing and the month of the AE end date is before the month of dosing date
5. An AE will not be a TEAE if the AE start day of month is missing and
 - a. The last day of the AE start month is before the dosing date
 - b. The first day of the AE start month is more than 4 days after dosing

All AE summaries will provide the number of patients reporting at least one AE and the total number of events reported.

The following summaries will be provided:

- A summary of the number and percentage of patients reporting an AE, including counts of TEAEs, IP-related TEAEs, SAEs and IP-related SAEs.

PAREXEL International

Blue Earth Diagnostics
BED-PSMA-301

Statistical Analysis Plan

- A summary of the number and percentage of patients reporting a TEAE by SOC, and PT
- A summary of the number and percentage of patients reporting a TEAE by Common Terminology Criteria for Adverse Events (CTCAE) grade, SOC and PT
- A summary of the number and percentage of patients reporting a TEAE by causality, SOC and PT

Adverse event summaries will be ordered in terms of decreasing frequency for SOC, and PT within an SOC and then alphabetically for SOC, and PT within SOC.

For each patient and each adverse event, the worst CTCAE Toxicity grade (Version 5) recorded will be attributed and used in the by-severity summaries. Similarly, the worst causality (most related to treatment) will be attributed and used in the by-causality summaries. If CTCAE is missing for, the missing category will be used as worst category. If causality is missing, the worst case will be assumed.

A by-patient listing of all adverse events (including non-treatment-emergent events) will be provided. This listing will include center, patient identifier, age, race, adverse event (SOC, PT, and verbatim term), date of onset, date of resolution, duration, CTCAE, seriousness, action taken, outcome and causality.

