10.4 Visit 3 (Day 2 to 4; Follow-up Visit)

1. Perform clinical review of imaging results and discussion of further procedures/treatments with the patient.
2. Record any AEs and changes in concomitant medication since Visit 2.
3. Perform a focused physical examination.
4. Perform repeat blood safety laboratory tests as outlined in [Section 9.2](#).
5. Perform 12-lead ECG.
6. Schedule patient to receive treatment within 45 days post-IP administration.

Notes:

- a. in cases where the rhPSMA-7.3 (¹⁸F) PET imaging results are not available at this visit, the imaging results and further procedures/treatment plan should be reviewed with the patient within 7 days after rhPSMA-7.3 (¹⁸F) imaging (this may be conducted by telephone at the clinician’s discretion).
- b. to ensure patient safety due to the COVID-19 pandemic, the post-IP safety follow-up (laboratory and ECG assessments and focused physical examination) may be conducted within 1 to 5 days post-IP administration.

Patients will remain in the study until the results of the histology or confirmatory imaging are obtained in order to satisfy the SoT.

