16.6 Analysis of Safety Endpoint(s)

Safety data will be summarized descriptively. For AEs and SAEs, the Medical Dictionary for Regulatory Activities (MedDRA) System Organ Class and Preferred Terms will be used to code the reported events. The number of events, number of patients with one or more event, and percentage of patients with one or more event will be provided for all AEs, related AEs, SAEs, and all related SAEs. For blood safety laboratory tests, vital signs and 12-lead ECG results, the change from baseline results will also be summarized. Focused physical examination findings will be summarized.

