3.2.4 Safety Variables

In all patients, safety evaluations will include AE monitoring and reporting from the time of informed consent throughout the study.

Vital sign assessments will also be conducted at screening and pre- and post-IP administration on the day of rhPSMA-7.3 (¹⁸F) injection.

In addition, a focused physical examination will be performed at screening and at the safety follow-up visit within 1 to 3 days post-IP administration (may occur within 1 to 5 days post-IP administration due to the COVID-19 pandemic), and a 12-lead ECG will be performed pre-IP administration on the day of rhPSMA-7.3 (¹⁸F) injection and at the safety follow-up visit within 1 to 3 days post-IP administration (may occur within 1 to 5 days post-IP administration due to the COVID-19 pandemic). Baseline blood safety laboratory tests, including hematology (full blood count), biochemistry (urea and electrolytes, liver function tests) and coagulation will be performed pre-IP administration on the day of rhPSMA-7.3 (¹⁸F) injection and repeated at the safety follow-up visit within 1 to 3 days post-IP administration (may occur within 1 to 5 days post-IP administration due to the COVID-19 pandemic).

4 STATISTICAL METHODS**4.1 Data Quality Assurance**

All tables, figures and data listings to be included in the report will be independently checked for consistency, integrity and in accordance with standard Parexel procedures.

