4.2 General Presentation Considerations

‘Baseline’ is defined as the last available pre-IP administration assessment.

‘End of Study’ is defined as the last available post-IP administration assessment.

PAREXEL International

Blue Earth Diagnostics
BED-PSMA-301

Statistical Analysis Plan

'Study Day' will be calculated relative to the date of rhPSMA-7.3 (¹⁸F) injection day, and is equal to:

- Assessment Date – IP Administration Date + 1 if the assessment date is on or after IP administration date.
- Assessment Date – IP Administration Date, if the assessment date is before IP administration date.

Continuous data will be summarized in terms of the mean, standard deviation (SD), median, minimum, maximum and number of observations, unless otherwise stated. Continuous data (e.g. counts) that are expected to be skewed will be presented in terms of the maximum, upper quartile, median, lower quartile, minimum and number of observations. The minimum and maximum will be reported to the same number of decimal places as the raw data recorded in the database. The mean, median, lower quartile and upper quartile will be reported to one more decimal place than the raw data recorded in the database. The SD will be reported to two more decimal places than the raw data recorded in the database. In case the rules result in more than four decimal places, the number of decimal places reported shall be four for any summary statistic, irrespective of the previous rules.

Categorical data will be summarized in terms of the number of patients providing data at the relevant time point (n), frequency counts and percentages. Any planned collapsing of categories will be detailed in the SAP text and the data displays.

Percentages will be presented to one decimal place. Percentages will not be presented for zero counts. Percentages will be calculated using n as the denominator. If sample sizes are small, the data displays will show the percentages, but any textual report will describe frequencies only.

Changes from baseline in categorical data will be summarized using shift tables where appropriate.

P-values greater than or equal to 0.001, in general, will be presented to three decimal places. P-values less than 0.001 will be presented as “<0.001”.

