4.15.2 Deaths, Serious Adverse Events, and Other Significant Adverse Events

Deaths, SAEs, and Other Significant AEs will be listed and summarized if numbers allow. The following summaries are planned.

- A summary of the number and percentage of TEAE leading to death
- A summary of the number and percentage of patients reporting a serious TEAE, by SOC and PT
- A summary of the number and percentage of patients with TEAEs leading to discontinuation of study treatment, by SOC and PT

The following listings will be created:

- A by-patient listing of all deaths that occurred during the study
- A by-patient listing of all SAEs
- A by-patient listing of all AEs leading to discontinuation of study treatment

Listings will follow the format described for AEs in Section 4.15.2.

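### AEs starting or worsening on Day 5 or 6, days on which the safety visit is still permitted, are left out of every TEAE-based table, and the partial-date rule uses a different limit

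*SAP*

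**What the plan says.** **TEAE window.** SAP 4.15.1 classifies an AE as treatment-emergent if it starts or worsens "on or after the date/time of IP administration and on or before Day 4". SAP 4.2 computes Study Day as "Assessment Date – IP Administration Date + 1 if the assessment date is on or after IP administration date".

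**Visit window.** Visit 3 is nominally Day 2 to 4. Protocol 10.4 adds that the laboratory, ECG and physical examination follow-up "may be conducted within 1 to 5 days post-IP administration" because of the pandemic. SAP 3.2.4 repeats this: it "may occur within 1 to 5 days post-IP administration due to the COVID-19 pandemic".

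**Partial dates.** SAP 4.15.1 treats an AE with a missing start day as treatment-emergent unless, among other conditions, this holds: "The first day of the AE start month is more than 4 days after dosing".

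**Tables limited to TEAEs.** In SAP 4.15.1 these are the tables by SOC and PT, by CTCAE grade and by causality. SAP 4.15.2 adds the fatal and discontinuation summaries and "A summary of the number and percentage of patients reporting a serious TEAE, by SOC and PT".

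**Outputs without the limit.** The overview in SAP 4.15.1 counts patients with an AE, SAEs and IP-related SAEs, but restricts the related-AE count to IP-related TEAEs. All AEs, SAEs and deaths are listed. The laboratory, ECG and examination summaries in SAP 4.15.3 and 4.15.4 run by visit.

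**Protocol commitment.** Protocol 16.6 states that the "percentage of patients with one or more event will be provided for all AEs, related AEs, SAEs, and all related SAEs". It names no time window.

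**The concern.** The safety visit exists to detect effects of the injection. Protocol 9.2 and 9.1.4 require clinically significant laboratory and examination changes to be reported as AEs. A laboratory change usually has no known onset before the sample was drawn. If the sample is taken on Day 5 or 6, as the plan permits, the resulting AE falls outside the TEAE window and out of the tables by SOC and PT, grade, causality and seriousness. The laboratory section nevertheless calls abnormalities at that same visit treatment-emergent, so one report can classify one finding in two ways.

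A non-serious, IP-related AE with onset on Day 5 or 6 has no planned tabulation as a related AE, although protocol 16.6 promises one. The overview counts it only among all AEs. SAP 4.17, which records changes from the protocol, does not mention this narrowing.

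**Working it through.** **Inputs.** Study Day rule (SAP 4.2); TEAE limit and partial-date rule (SAP 4.15.1); visit windows (protocol 10.4, SAP 3.2.4).

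**Formula.** On or after the injection date, Study Day = days post-IP + 1.

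**Step 1, the plan's own figure.** A visit 1 to 3 days post-IP gives 1 + 1 = 2 to 3 + 1 = 4. This is the Day 2 to 4 label in protocol 10.4, so the conventions agree.

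**Step 2, the extended window.** A visit 1 to 5 days post-IP gives Day 2 to 5 + 1 = Day 6.

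**Step 3, the three rules day by day.** The last column applies the partial-date limit to the first day of the start month.

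| Days post-IP | Study Day | Safety visit | Fully dated onset is a TEAE | Partial-date rule excludes |
|---|---|---|---|---|
| 0 | 1 | injection day | yes | no |
| 1 | 2 | nominal | yes | no |
| 2 | 3 | nominal | yes | no |
| 3 | 4 | nominal | yes | no |
| 4 | 5 | extension | **no** | **no** |
| 5 | 6 | extension | **no** | yes |
| 6 | 7 | not permitted | no | yes |

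The gap between the visit window and the TEAE window is 6 − 4 = 2 days, out of five permitted visit days (Days 2 to 6).

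**Step 4, the partial-date mismatch.** More than 4 days after dosing means 5 or more, which is Day 6 onward. Take an injection on 28 January. Then 1 February is 4 days later, which is Day 5. An AE recorded as starting in February with the day missing cannot have begun by Day 4, yet it is a TEAE. The same AE recorded as 1 February is not. The two limits differ by one day.

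**Step 5, where a Day 6 finding goes.** Take a non-serious, IP-related laboratory AE first found at a Day 6 visit and dated to that visit.

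| Output | Included? |
|---|---|
| Tables by SOC and PT, CTCAE grade and causality | no |
| Overview: patients with an AE | yes |
| Overview: TEAEs and IP-related TEAEs | no |
| Listing of all AEs | yes |
| Visit 3 laboratory summary and shift table | yes |

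If the event were serious, the overview would count it as an SAE and an IP-related SAE and it would be listed. The serious-TEAE table by SOC and PT would omit it.

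**Step 6, medications.** SAP 4.7 lists but does not summarise medications and procedures that start after Day 4. Treatment of a late-visit finding is therefore also left out of the summaries.

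**The case against.** The best defence is that a short fixed window is a deliberate and reasonable choice. The SAP revision history shows that version 3.0 moved the limit from Visit 3 to Day 4. Day 4 matches the nominal visit window and the three-day period in the AE follow-up wording of protocol 9.1.9. It gives every patient the same time at risk. The product is a single microdose, its isotope has a half-life of 109.8 minutes, and it is not designed to have pharmacological activity. The SAP may also modify the protocol's analyses. All of this supports a fixed window. It does not explain why the limit stops short of a visit day that the SAP itself allows, or why the partial-date limit differs.

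A reader might infer more than the documents support:

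- **That everything found at a late visit is lost.** Classification follows the date of onset or worsening, not the visit date. An AE that began on Days 1 to 4 and is first reported on Day 6 is a TEAE.
- **That later deaths vanish.** A death after Day 4 from an AE that began by Day 4 stays in the fatal-TEAE summary, and all deaths are listed.
- **That SAEs go uncounted.** The overview counts SAEs and IP-related SAEs with no window. Only the breakdown by SOC and PT is restricted.
- **That rates are understated only in patients who used the extension.** A Day 5 symptom is excluded whether Visit 3 was on Day 2 or Day 6. Only findings dated to the visit itself are lost specifically in patients seen late.

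The partial-date mismatch is also rare. It needs a missing start day and dosing exactly four days before the start month begins, and it errs toward inclusion.

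**Conclusion.** The mismatch stands in its limited form. AEs with onset or worsening on Day 5 or 6 are absent from all TEAE-based tables although the safety visit may fall on those days. The laboratory shift table and the partial-date rule do not follow the same limit. IP-related non-serious AEs outside the window have no related-AE count, contrary to protocol 16.6.

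The effect is a small possible under-count in the TEAE tables. No event disappears from the report, and no efficacy result is touched. Two of five permitted visit days is a share of calendar days, not of patients or events. The documents do not say how many visits fell on Day 5 or 6, so no event count can be derived.

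The conclusion assumes that a change first detected at a visit is dated to that visit, since the SAP gives no other onset rule. For ECG it also assumes that clinically significant changes are reported as AEs: protocol 9.1.5 covers ECG, but its reporting sentence names only vital signs.

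**What to change.** Choose one limit and use it throughout.

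1. **Either** set a fixed TEAE limit through Day 6 for all patients, **or** keep Day 4 and add a supplementary AE table through Day 6. Do not tie the limit to each patient's actual visit date, because windows ending anywhere from Day 4 to Day 6 would give patients unequal time at risk.
2. Align the partial-date rules. A Day 6 limit excludes start months beginning more than 5 days after dosing; a Day 4 limit excludes those beginning more than 3 days after.
3. Apply the same limit to the medication and procedure cut-off in SAP 4.7.
4. Tabulate all IP-related AEs without a window, as protocol 16.6 states.
5. Record the choice and its reason in SAP 4.17.

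The cost is SAP wording, one derivation and one or two extra tables. No new data are needed, because Appendix 1 of the protocol already schedules AE recording through the follow-up procedures. The downside is that a few more background events will be counted.
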